#### 9.3.4.2. Analysis

Unless otherwise stated analysis of time to culture conversion will be summarized as follows:

1. Basic statistics of time to conversion
2. Number of observations, number of censored observations, number at risk (by visit)
3. Hazard ratio (ALIS + background regimen: ELC + background regimen) and corresponding 95% CIs,
4. Kaplan-Meier plot will be provided
5. A Cox regression model will be applied to calculate the hazard ratio. The model includes effects for treatment and stratification variable (history of MAC lung infection, initial or subsequent).

#### 9.3.5. Time to First Negative Culture

##### 9.3.5.1. Variable Description

Time to first negative culture is the number of months from the date of first dose of study drug(s) to the date of first MAC culture negative post-baseline.

Time to first negative culture (months) =

$$(\text{date of first MAC culture negative} - \text{date of first dose of study drug(s)} + 1) / 28^*$$

\* rounded to the nearest month

Months 1 through Month 7 will be presented. Subjects without MAC culture negative are considered censored. Time of censoring is set to the last visit with available culture assessment up to and including Month 7.

##### 9.3.5.2. Analysis

The same statistics will be presented as described in [Section 9.3.4.2](#).

#### 9.3.6. Microbiology Assessment

Mycobacteria isolate species (*Mycobacterium avium* complex overall, *M. avium*, *M. intracellulare*, and other speciated and unspciated MAC) are the variables of interest.

Drug susceptibility of MAC treatment will also be presented.

MIC ( $\mu\text{g/mL}$ ) is reported in powers of 2, eg,  $0.125 = 2^{-3}$ ,  $0.25 = 2^{-2}$ , ... ,  $64 = 2^6$ , etc. Therefore, the values that may appear in this table are 0.125, 0.25, 0.5, 1, 2, 4, 8, 16, 32, 64, 128 and >128. The MIC will be tabulated for each reported MIC value including any values not reported between the minimum and maximum values.

If there are multiple assessments collected for MIC assessment for one visit, the maximum MIC value will be used.

All variables will be tabulated by treatment (individual and overall) at each timepoint.

The denominator for percentages will be the number of subjects with available data.

#### **9.3.6.1. MAC isolates with clarithromycin MIC $\geq$ 32 $\mu\text{g/mL}$**

Drug susceptibility to macrolide (ie. AZI) is based on clarithromycin MICs and will be categorized as follows based on Clinical and Laboratory Standards Institute interpretive criteria (Clinical and Laboratory Standards Institute Guideline M24, 2018):

- Sensitive: MIC  $\leq$  8  $\mu\text{g/mL}$
- Intermediate: MIC = 16  $\mu\text{g/mL}$
- Resistant: MIC  $\geq$  32  $\mu\text{g/mL}$

For clarithromycin, MICs will be reported up to 32  $\mu\text{g/mL}$ . Values above 32  $\mu\text{g/mL}$  will be reported as  $>$  32  $\mu\text{g/mL}$ .

For each timepoint and, additionally, the maximum MIC for each subject (Month 1 to Month 6), the following summary statistics will be calculated:

- Number and percent of subjects per reported MIC value
- Number and percent of subjects per category indicating resistance: Sensitive, Intermediate, Resistant
- Mean, range, MIC50, MIC90
- Change from baseline (ratio of geometric means)
- Number of subjects with change from baseline  $\geq$  4 fold

MIC50 and MIC90 are the antibiotic concentrations required to inhibit growth of 50% and 90% of the isolates, respectively. This can be calculated as 50th-percentile (ie, median) and 90th percentile in SAS using the percentile definition 3 (PCTLDEF=3).

#### **9.3.6.2. MAC isolates with amikacin MIC $\geq$ 128 $\mu\text{g/mL}$**

Drug susceptibility to amikacin will be reported as described for macrolide in [Section 9.3.6.1](#), with the following deviation:

For amikacin, MICs will be reported up to 128  $\mu\text{g/mL}$ . Values above 128  $\mu\text{g/mL}$  will be reported as  $>$  128  $\mu\text{g/mL}$ .

The breakpoints for inhaled liposomal amikacin are

- Sensitive: MIC  $\leq$  64  $\mu\text{g/mL}$
- Resistant: MIC  $\geq$  128  $\mu\text{g/mL}$

The summaries of this secondary endpoint will include the number and percentage of subjects in each category (subjects who developed a resistance vs subject who did not develop a resistance) will be presented by treatment group.

Number of subjects who developed a resistance will be plotted over time by timepoint and cumulative over time.

### 9.3.7. Recurrence

#### 9.3.7.1. Variable Description

##### Baseline MAC species/genome

The baseline MAC species/genome is the species grown in sputum samples collected at Baseline/Day 1. If Baseline/Day 1 is MAC culture negative or missing, the Screening samples will be taken instead. Screening samples are MAC culture positive, as only subjects with MAC culture positive at Screening are included in the study. If 2 different species/genomes were cultured at baseline, both are considered the baseline MAC species/genome.

##### Recurrence: Relapse

A relapse is defined as a positive culture that is the **same** species and genome as cultured at baseline subsequent to culture conversion.

If more than one species/genome are found, the subject shows a relapse if any of the cultures match the species/genome(s) at baseline.

The positive culture is defined as at least 1 MAC positive culture in agar media or positive cultures in broth media in at least 2 consecutive visits. Missing MAC culture assessments which are imputed to positive do not contribute to recurrence.

Note: The definition of positive culture that establishes recurrence is different from the definition of MAC culture positive used for culture conversion.

##### Recurrence: New MAC Infection

A new MAC infection is defined as a positive culture that is **different** than cultured at baseline (different species, or same species but different genome) subsequent to culture conversion.

If more than one species/genome are found, at least one of the species/genomes must be different than the baseline species/genome(s).

The positive culture is defined as at least 1 positive culture in agar media or positive cultures in broth media in at least 2 consecutive visits.

If a subject shows both relapse and new MAC infection at the same timepoint, relapse is counted for this timepoint only.

#### 9.3.7.2. Analysis

The proportion of subjects who had relapse, and the proportion of subjects with new MAC infection at any timepoint during the study and treatment will be analyzed. Recurrence will be analyzed at the subject level and by timepoint (Month 3 to Month 7).

Number of subjects and percentages will be provided. The denominator is always the respective number of subjects at risk, ie, subjects with culture conversion.

### 9.3.8. Subgroup Analysis

Treatment effect across major subgroups on the QOL-B Respiratory Symptoms Month 7, PROMIS Fatigue Month 7, and Conversion by Month 6 will be summarized. Subgroup factors are shown in the list below:

- Age: < 65 years, ≥ 65 years
- Gender: Female, Male
- Race: American Indian or Alaska Native, Asian, Black or African American, Native Hawaiian or Other Pacific Islander, White (races with small counts may be excluded from summaries)
- Stratification variable 'History of MAC lung infection': initial, subsequent
- Stratification variable 'Region': North America, Europe, and Rest of World
- MAC infection at baseline: Mycobacteria isolate species (*Mycobacterium avium* complex overall, *M. avium*, *M. intracellulare*), and other speciated and unspciated MAC)

The microbiological assessment analysis (MIC and susceptibility) will be summarized for the following subgroups:

- Stratification variable 'Region': North America, Europe, and Rest of World
- MAC infection at baseline: Mycobacteria isolate species (*Mycobacterium avium* complex overall, *M. avium*, *M. intracellulare*), and other speciated and unspciated MAC)

Subgroup analysis will use the same analytical approach as in the secondary endpoint analyses. Statistical modeling will not include history of MAC lung infection as covariate. Plots will not be generated for subgroups.

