### 7.2. Multiple Comparisons and Multiplicity

All summaries presented within the scope of this SAP will be descriptive without multiplicity adjustment. Ninety-five percent confidence intervals for estimation of treatment differences and associated p-values will not be adjusted for multiplicity. There is no intention to make inferences based on these statistics, as their value is nominal.

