#### **9.1.2. Usage of the covariates in the statistical models**

The study was randomized with two stratification strata: history of MAC disease and region (North America, Europe, and Rest of World). The statistical modeling using these categorical variables would imply a total of 12 strata combinations: 2 (treatments) \* 2 (history of MAC disease) \* 3 (geographical regions). Since the sample size for this study is 100 subjects, it is expected for some strata to have empty cells, resulting in inestimable parameters. Therefore, geographical region is not used in the model for all analyses included in this SAP. Impact of this variable is addressed in the subgroup analyses.

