### **9.3.1.2. Analysis**

The endpoint of interest is the proportion of subjects achieving culture conversion by Month 6 as this is the last month of exposure to study medication in this study. The reporting will be presented based on the ITT analysis set and will be provided by randomized treatment group.

The analysis model is the Standardized Logistic Regression (SLR), the model includes response variable, ie conversion status by Month 6 and the following independent variable (stratum at randomization):

- history of MAC lung infection, (initial or subsequent)

The summaries will include:

1. Estimation of group proportions of subjects achieving conversion by Month 6 and difference of these proportions between the treatment groups together with corresponding 95% CIs will utilize the above described SLR model.

The estimation obtained from SLR will be based on the standardized procedure described in [Steingrimsson et al\[13\]](#), the SAS macro %Margin, version 2.0 (or later), provided SAS Institute ([see SAS note <https://support.sas.com/kb/37/228.html>](#)) will be used for implementation.

2. Descriptive statistics, ie, number/frequency of subjects with available assessments and conversion status (ie, rules 1 through 4) will be applied as described in [Section 9.3.1.2.1](#).

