## 10.5. Subgroup Analysis

Subgroup analyses will be performed on the following:

1. QOL-B non-respiratory symptoms Month 7
2. Subjects meeting WSMC QOL-B Month 7
3. Subjects meeting WSMC PROMIS Fatigue Month 7

Subgroup factors are shown in the list below:

- Age: < 65 years,  $\geq$  65 years
- Gender: Female, Male
- Race: American Indian or Alaska Native, Asian, Black or African American, Native Hawaiian or Other Pacific Islander, White (races with small counts might be excluded from summaries)
- Stratification variable 'History of MAC lung infection': initial, subsequent
- Stratification variable 'Region': North America, Europe, and Rest of World
- MAC infection at baseline: Mycobacteria isolate species (*Mycobacterium avium* complex overall, *M. avium*, *M. intracellulare*), and other speciated and unspciated MAC)

Subgroup analysis will use the same analytical approach as the main analysis. Statistical modeling will not include history of MAC lung infection as covariate.

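### In small subgroups, the covariate-free SLR for Month 6 conversion is in effect a Wald interval: it covers below its nominal 95% and mishandles arms at 0% or 100%

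*SAP*

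**What the plan says.** - **Main analysis, SAP 9.3.1.2.** Arm proportions and their difference come from SLR: "difference of these proportions between the treatment groups together with corresponding 95% CIs will utilize the above described SLR model". The one covariate listed is "history of MAC lung infection, (initial or subsequent"). A SAS margins macro is named; its variance method is not stated.
- **Subgroups, SAP 9.3.8.** "Subgroup analysis will use the same analytical approach as in the secondary endpoint analyses". History of MAC infection is dropped from the models. The factors are age, gender, race, history, region and baseline MAC species. Races with small counts may be left out; no count is specified and no other factor has such a rule.
- **Region, SAP 9.1.2.** Region is in no model, and its influence is left to the subgroup analyses.
- **WSMC responders, SAP 10.5.** "Subgroup analysis will use the same analytical approach as the main analysis", again without history.
- **Imputation.** Appendix I pools conversion results over 50 imputations by Rubin's rule. For WSMC, 10.3.2 averages the imputed changes to one value per subject.
- **Status of the intervals, SAP 7.2.** "Ninety-five percent confidence intervals for estimation of treatment differences and associated p-values will not be adjusted for multiplicity", followed by "There is no intention to make inferences based on these statistics, as their value is nominal".

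**The concern.** With history removed and region never included, treatment is the only term left in the subgroup model. Such a model borrows nothing across subjects, so its large-sample standard error is the ordinary Wald one. That is adequate with 50 per arm but weak in a small subgroup.

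If every subject in an arm converts, or none does, the logistic estimate for that arm does not exist. The software then reports a standard error near zero, and the table can show an arm estimate of 100% with limits of 100% and 100%.

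A reader of the subgroup tables could then see a difference that excludes zero only because of the interval method. SAP 9.1.1 also attaches nominal p-values to efficacy differences reported with confidence intervals, and the SAP relies on these tables to show any effect of region.

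**Working it through.** **Inputs.** From the documents: 100 subjects, 50 per arm, 1:1 allocation, conversion 50–70% (SAP 4.3.1 and 4.4) and nominal 95% intervals (SAP 7.2). Assumed: subgroup sizes, arm rates of 80% and 90%, and delta-method errors in the macro.

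**1. The plan's own figure.** The SAP gives no coverage figure other than the nominal 95%. The figure that fixes the sample size is at least 80% power at N = 100 for converters versus non-converters. Take polyserial correlation 0.40 and point-biserial r = 0.40·φ(z_p)/√(p(1−p)). With p = 0.70, r = 0.40 × 0.348/0.458 = 0.304. With 20% missing, N = 80 and λ = r/√(1−r²)·√N ≈ 2.85, so power is 0.803. With p = 0.50 and nothing missing it is 0.915. The stated power reproduces. It does not speak to subgroup intervals.

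**2. SLR without covariates equals Wald.** In a treatment-only logistic model the fitted proportion is x/n and the logit has variance 1/(n·p(1−p)). The delta method multiplies this by [p(1−p)]², which gives p(1−p)/n. For 7/10 versus 5/10, SE = √(0.021 + 0.025) = 0.2145. The fitted logistic model also gives 0.2145. For 6/8 versus 4/8 both give 0.2339.

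**3. Coverage of the interval for the difference.** Two independent binomials were enumerated exactly, with true rates 50/50, 60/60, 70/70, 70/50, 80/50, 80/60 and 90/70%.

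| Per arm | Wald, 70 vs 50% | Wald, all seven pairs | Newcombe, all seven pairs |
|---|---|---|---|
| 5 | 89.0% | 81.0–92.2% | 93.8–98.2% |
| 6 | 87.6% | 83.6–93.6% | 92.9–97.5% |
| 8 | 91.2% | 90.5–93.5% | 92.3–97.5% |
| 10 | 92.2% | 90.5–93.9% | 94.4–96.3% |
| 16–17 | 92.6–94.2% | 92.6–94.3% | 93.7–96.1% |
| 50 | 94.2% | 94.2–94.7% | 94.3–95.4% |

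At 5 and 6 per arm, 12 of the 14 Wald results lie between 81% and 90%. The exceptions are 92.2% (70/70 at 5) and 93.6% (80/50 at 6). Three equal regions would give 100/3/2 ≈ 16.7 per arm.

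When both arms truly convert at 60%, the Wald interval excludes zero with probability 1 − 0.863 = 13.7% at 6 per arm and 1 − 0.908 = 9.2% at 10. Newcombe gives 6.3% and 4.0%.

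**4. Arms at 0% or 100%.** Take 8/8 versus 5/8, difference 0.375.
- Wald: SE = √(0 + 0.625 × 0.375/8) = 0.171, so the interval is 0.375 ± 0.335, or 4 to 71 points. The 8/8 arm adds nothing.
- Newcombe: the Wilson limits are 0.676–1.000 and 0.306–0.863. Lower limit: 0.375 − √(0.324² + 0.238²) = −0.027. Upper limit: 0.375 + 0.319 = 0.694. The interval is −3 to 69 points.

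With one extreme arm the difference keeps some width: 5/5 versus 3/5 gives −3 to 83 points, while the logistic SE of the 5/5 arm itself is about 0.000006. The difference has zero width only if both arms are extreme: 5/5 versus 5/5 gives 0 to 0 by Wald and −43 to 43 by Newcombe.

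At 5 per arm and 70/50%, the chance that an arm is extreme is 0.7⁵ + 0.3⁵ = 0.1705 and 2 × 0.5⁵ = 0.0625. At least one arm is extreme with probability 1 − 0.8295 × 0.9375 = 22%. Both are extreme with probability 0.1705 × 0.0625 = 1.1%.

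**The case against.** The strongest reply is that little hangs on these intervals. SAP 7.2 calls them nominal and disclaims inference, no subgroup result feeds a decision rule, and the primary objective is psychometric. This stands and limits the weight of the point. It does not make an 88% interval a good description when it is labelled 95%.

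Second, no document says how large any subgroup will be. Factors with two or three levels could leave 16 to 25 per arm, where the shortfall is small. This also stands. A reader might take the remark in SAP 9.1.2 that "it is expected for some strata to have empty cells, resulting in inestimable parameters" as a forecast of tiny subgroups. It is not: it concerns the 12 combinations of treatment, history and region, and explains why region is left out of the models. Only race is acknowledged in 9.3.8 as possibly sparse, and there exclusion is allowed.

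Third, imputation can widen the interval. Rubin's rule adds between-imputation variance where a subject's conversion status is imputed, so the exact Wald form and exact zero width hold only in subgroups with no imputed status. For WSMC this reply does not apply, because 10.3.2 uses one averaged value per subject.

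Finally, a reader might infer that one arm at 0% or 100% collapses the interval for the difference. It does not. One extreme arm collapses that arm's own interval and makes the interval for the difference too narrow.

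**Conclusion.** The point holds in a limited form. Followed as written, SAP 9.3.8 gives a Wald-type interval for subgroup differences in conversion. The undercoverage is material at about 5–6 per arm (mostly 81–90%), modest at 8–10 (90.5–94%) and slight at 16–17 (about 93–94%). It would be wrong to conclude that all the subgroup intervals are badly off, or that the full-sample analysis is affected: with 50 per arm coverage is 94–95%.

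The plan has no rule for an arm at 0% or 100% and no provision for small subgroups other than race.

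The conclusion rests on three assumptions: delta-method errors in the macro, subgroup sizes that the documents do not give, and little or no imputed status in the subgroup. The lowest coverage figures also use a 90% arm rate, above the 50–70% in the documents; within 50–70%, coverage is 85–92% at 5–6 per arm. Because the intervals are nominal and descriptive, this is a cheap improvement to reporting and does not threaten the study's conclusions.

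**What to change.** **SAP 9.3.8.** Keep SLR for the full sample. For conversion in subgroups, report Newcombe (or Agresti-Caffo) 95% intervals for the difference and Wilson intervals for each arm, all on the status set by rules 1–4 of 9.3.1.2.1, so that the arm estimates subtract to the reported difference. If imputed subjects should be kept, use Agresti-Caffo-type estimates for both the arms and the difference in each imputed data set and pool them by Rubin's rule. Choose one route in advance.

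**SAP 10.5.** Use the same intervals for the WSMC responder subgroups, on the single per-subject responder status that follows from 10.3.2. Rubin pooling and rules 1–4 do not apply there.

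**Cost.** A few sentences in the SAP and a few lines of code. Subgroup intervals will generally be wider, and their method will differ from the full-sample SLR, which a table footnote should say. The rule 1–4 route also omits subjects whose status would otherwise be imputed, so its denominators should be shown.

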## 10. EXPLORATORY OBJECTIVES

### 10.1. Analysis

Unless otherwise stated, all summaries pertaining to exploratory endpoints will utilize available data. Summaries will be presented by treatment group and by visit, as appropriate.

### 10.2. QOL-B Patient-reported Non-respiratory Symptoms

#### 10.2.1. Variable Description

The non-respiratory symptoms domain from QOL-B are

- Physical Functioning Domain
- Role Functioning Domain
- Vitality Domain
- Emotional Functioning Domain
- Social Functioning Domain
- Health Perceptions Domain

Derivations of domains are described in [Section 9.3.2.1](#).

#### 10.2.2. Analysis

**Endpoint:** Change from baseline to Month 7 in the QOL-B non-respiratory domains

**Timepoint:** Change between baseline and Month 7

**Type of endpoint:** Continuous

Summaries will include:

1. Basic statistics of actual values and change from baseline
2. LS-mean of change from baseline, differences of LS-mean changes from baseline (ALIS + background regimen – ELC + background regimen) estimates and corresponding 95% CIs derived from ANCOVA model.

The ANCOVA model will include change from baseline as response variable and treatment, baseline value, and history of MAC lung infection (initial or subsequent) as independent variables.

The basic summaries will be also provided for all other timepoints.

### 10.3. Subjects meeting WSMC

#### 10.3.1. Variable Description

Within-subject meaningful change (WSMC) from baseline to Month 7 is one threshold on the QOL-B Respiratory Symptoms Domain Score and one threshold on the PROMIS

Fatigue Score and their estimation is described in the VAP. The thresholds will be provided after unblinding of the study and will be provided exclusively for the revised scales, therefore this analysis will be included in the CSR appendix.

The WSMC threshold values will be used to categorize subjects into two categories at Month 7: subjects meeting the criteria of change from baseline to Month 7 meeting or exceeding (in the improved direction) the threshold or not.

### 10.3.2. Analysis

**Endpoint:** Proportion of subjects meeting the within-subject meaningful change threshold as reflected in PRO changes scores in patient-reported symptoms (as assessed by QOL-B Respiratory Symptoms domain and PROMIS F-SF 7a)

**Timepoint:** Change between baseline and Month 7

**Type of endpoint:** Categorical

Summaries will include:

1. Basic summary statistics: number of subjects in each category
2. Difference of proportions (ALIS + background regimen – ELC + background regimen)

Estimation of proportions and differences of proportions together with corresponding 95% CIs will utilize SLR of the proportions adjusted for stratification variable (history of MAC lung infection, initial or subsequent)

The estimation obtained from SLR will be based on the standardized procedure described in [Steingrimsdottir et al\[13\]](#), the SAS macro %Margin, version 2.0 (or later), provided SAS Institute (see SAS note <https://support.sas.com/kb/37/228.html>) will be used for implementation.

Basic summaries will be performed on the observed data (including retrieved data after ALIS/ELC discontinuation), while inferential summaries (SLR) on the imputed. Specifically, for subjects with imputed QOL-B Respiratory Symptoms score data, change from baseline values will be averaged across 50 available imputations. For PROMIS Fatigue, additionally, averaged values will be rounded to the nearest integer. This method will ensure consistency between data usage in this and anchor-based analysis.

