4.1.1. Inclusion Criteria

Subjects must satisfy all of the following criteria to be included in the study:

1. Male or female ≥ 18 years of age (19 years or older in South Korea)
2. Current diagnosis of MAC lung infection. MAC or mixed infection with MAC as the dominant species is allowed, with MAC as the intended organism for treatment
3. Positive sputum culture for MAC within 6 months prior to Screening
4. Positive sputum culture for MAC at Screening
5. A chest CT scan, read locally, within 6 months prior to Screening to determine presence and size of pulmonary cavities. Subjects who do not have a chest CT scan within 6 months prior to Screening will be required to obtain a chest CT scan, read locally, during Screening
6. In the Investigator's opinion, documented respiratory signs/symptoms at Screening that are attributable to the current MAC lung infection
7. An average QOL-B respiratory domain score of ≤ 85 based on scores at Screening and on the day of enrollment prior to randomization
8. In the Investigator's opinion, underlying lung disease (eg, COPD, bronchiectasis) have been managed according to best local standard of care, and on stable maintenance therapy for a minimum of 4 weeks prior to randomization
9. Willingness and ability to adhere to prescribed study treatment during the study
10. Ability to produce (spontaneously or with induction) approximately 2 mL of sputum for mycobacteriology at Screening
11. WOCBP (ie, fertile following menarche and until becoming post-menopausal unless permanently sterile) and fertile men (ie, all men after puberty unless permanently sterile by bilateral orchidectomy) agree to practice a highly effective method of birth control from Day 1 to at least 90 days after the last dose. Examples of such birth controls are:
 - true abstinence (refraining from heterosexual intercourse during the entire study),
 - copper IUD,
 - hormonal methods (levonorgestrel-releasing intrauterine system, progestogen implant, combined oral contraceptive pill [combined with barrier method]),
 - exclusive homosexual relationship, or
 - sole male partner who has undergone surgical sterilization with confirmation of azoospermia at least 3 months post procedure while participating in the study.
12. Provide signed informed consent prior to administration of study drugs or performing any study related procedure
13. Be able to comply with study drugs use, study visits, and study procedures as defined by the protocol

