#### **9.3.2.2. Analysis**

The analysis of change from baseline to Month 7 in respiratory symptom score (as assessed by QOL-B) will be summarized based on subjects in the ITT analysis set by treatment group.

The analysis model is the ANCOVA, the model includes response variable, ie, change from baseline to Month 7 and the following independent variables:

- history of MAC lung infection, (initial or subsequent)

- baseline QOL-B Respiratory domain score

The regression coefficient for treatment group in the ANCOVA is equal to the estimated population-level average treatment effect of  $\mu_{\text{ALIS}} - \mu_{\text{ELC}}$ ; this estimate will be used in Wald tests deriving p-value for the difference between the treatment groups. The p-value is nominal as the study is not a hypothesis testing and further is not powered for this comparison.

The summaries will include:

1. LS-mean of change from baseline to Month 7, differences of LS-mean changes from baseline (ALIS + background regimen minus ELC + background regimen) estimates and corresponding 95% CIs derived from ANCOVA model.
2. Descriptive statistics by timepoint with corresponding change from baseline.

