## 11.2. PGI-S

### 11.2.1. PGI-S Respiratory

The PGI-S Respiratory score is a categorical rating of symptom severity. The scale ranges from 1 = not at all to 5 = extremely severe ([Appendix G](#)). Negative change from baseline indicates improvement (post therapy score – baseline score < 0).

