#### 11.2.2.1. Analysis of PGI-S Scores

Change from baseline to Month 7 in PGI-S scores will be analyzed similarly to QOL-B respiratory domain, see [Section 9.3.2.2](#) for details.

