#### Categorical Analysis

The following categories for change from baseline will be defined:

- Very much better if change from baseline = -4
- Much better if change from baseline = -3
- Better if change from baseline = -2
- Somewhat better if change from baseline = -1
- No changed if change from baseline = 0
- Somewhat worse if change from baseline = 1
- Worse if change from baseline = 2
- Much worse if change from baseline = 3
- Very much worse if change from baseline = 4

In addition, the following simplified categories for change from baseline will be defined:

- Improved (Very much better / Much better / Better / Somewhat better) if change from baseline  $\leq -1$
- No change if change from baseline = 0
- Worse (Very much worse / Much worse / Worse / Somewhat worse) if change from baseline  $\geq 1$

Within-subject change from baseline to Month 7 are summarized as follows:

- Proportion of subjects in each PGI-S category for change from baseline to Month 7.
- Proportion of subjects in each PGI-S simplified category (Improved/No change/Worsen) for change from baseline to Month 7 ( $\leq -1$ , 0,  $\geq 1$ ) by treatment group and pooled.
- Between treatment groups comparison of the proportion of subjects in PGI-S Improved simplified category (i.e., change from baseline to Month 7  $\leq -1$ ) using Cochran-Mantel-Haenszel test stratified by history of MAC lung infection (initial or subsequent).

For the purpose of this analysis, PRO data for subjects with missing data, imputations of change from baseline values will be averaged across 50 available imputations and rounded to the nearest integer to obtain a single value per subject.

### 11.3. Culture Conversion by Month 7

The endpoint of interest is the proportion of subjects achieving culture conversion by Month 7. The reporting will be presented based on the ITT analysis set and will be provided by randomized treatment group.

Converters by Month 7 are subjects who have a negative culture at Month 7, and have achieved culture conversion by one of the following:

- MAC culture negative at Month 6 after adjustment for non-productive sputum, or
- Missing MAC culture at Month 6, and one of the below:
  - Achieved culture conversion (2 consecutive monthly negative sputum cultures), have negative culture after conversion, do not have recurrence after conversion, with at most 1 missing sputum assessment at or before Month 5, or
  - Negative culture at Month 5

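### The WSMC and PGI-S 'Improved' arm comparisons leave out the baseline score of the same PRO, giving up a modest amount of precision that data already collected could recover

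*SAP*

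**What the plan says.** SAP 10.3.1 splits subjects into "subjects meeting the criteria of change from baseline to Month 7 meeting or exceeding (in the improved direction) the threshold or not". SAP 10.3.2 then estimates the responder proportions, their arm difference and 95% CIs by standardised logistic regression (SLR): the estimation "will utilize SLR of the proportions adjusted for stratification variable (history of MAC lung infection, initial or subsequent".

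For PGI-S, SAP 11.2.2.1 defines 'Improved' as a change of -1 or lower and compares arms "using Cochran-Mantel-Haenszel test stratified by history of MAC lung infection (initial or subsequent". It names a test and does not itself ask for a difference with an interval. On the scale, "The scale ranges from 1 = not at all to 5 = extremely severe".

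The mean-change analyses that compare arms do adjust for baseline:
- SAP 9.3.2.2 lists "baseline QOL-B Respiratory domain score" in the ANCOVA, and 9.3.3.2 applies the same approach to PROMIS fatigue.
- SAP 10.2.2 uses "treatment, baseline value, and history of MAC lung infection (initial or subsequent) as independent variables", and 11.1.5 does the same for the other PROs.
- SAP 11.2.2.1 itself states: "Change from baseline to Month 7 in PGI-S scores will be analyzed similarly to QOL-B respiratory domain".

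SAP 9.1.2 explains why region is left out of the models (empty cells). It gives no reason for leaving out a baseline score. SAP 7.2 makes all results descriptive, with nominal p-values.

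**The concern.** Whether a subject reaches a fixed gain depends partly on where that subject started. For PGI-S this holds by construction: a subject at level 1 cannot fall by a point and so can never be 'Improved'. Protocol 4.1 sets no fatigue threshold for entry, so such subjects can be enrolled. For QOL-B and PROMIS the dependence comes from regression to the mean and from room to improve.

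Randomization is stratified by region and MAC history only (SAP 4.4). With about 50 subjects per arm, baseline scores will differ between arms by chance, and neither responder comparison corrects for it. Appendix I uses baseline in the imputation models, but that only fills missing values.

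At stake is the precision of the responder differences. The SLR is already specified and can take the covariate. The paper cited for it is, by its title, about gaining precision from prognostic baseline variables.

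**Working it through.** **The plan's own figure.** SAP 4.3.1 claims at least 80% power with 100 subjects, for converters versus non-converters. With polyserial correlation ρ = 0.40 and conversion rate p, point-biserial r = ρ·φ(z_p)/√(p(1-p)) and d = r/√(p(1-p))/√(1-r²).
- At p = 0.5: r = 0.40 × 0.399/0.5 = 0.319 and d = 0.638/√(1 - 0.102) = 0.674. Power is 0.915 with no missing data and 0.845 with 20% missing (noncentral t).
- The lowest case, p = 0.7 with 20% missing, gives 0.803.

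The claim reproduces. It concerns a different comparison and does not change here. No power or precision is stated for either responder comparison.

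**Precision as planned.** With 50 per arm, SE = √(2p(1-p)/50). For responder rates of 30% and 50% this is 0.092 and 0.100, so the 95% CI half-width is 18.0 to 19.6 percentage points.

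**Inputs.** From the documents: 50 per arm, nine QOL-B respiratory items scored 1 to 4 on a 0-100 scale (one step = 100/27 = 3.7 points), the entry limit of 85, and PGI-S 1 to 5. Assumed: baseline distributions, correlations, responder rates and the WSMC threshold.

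**WSMC, simulation A.** 1,500 trials per scenario; baseline mean 58, SD 16, truncated at 85; responder = two steps (7.4 points). SE of the SLR risk difference without and with baseline:

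| Pre-post correlation | Without | With | SE reduction |
|---|---|---|---|
| 0.4 | 0.0986 | 0.0920 | 6.7% |
| 0.5 | 0.0995 | 0.0929 | 6.6% |
| 0.6 | 0.1024 | 0.0970 | 5.3% |
| 0.7 | 0.0975 | 0.0946 | 3.0% |

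At 0.4 the CI half-width goes from 1.96 × 0.0986 = 19.3 points to 1.96 × 0.0920 = 18.0. The variance ratios run from 0.872 to 0.941, worth about 15 to 6 extra subjects per 100 (1/0.872 and 1/0.941).

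**WSMC, simulation B.** 50 per arm, responder rate about 44%, indexed by baseline-change correlation. The last column is the shift in the unadjusted difference for a baseline imbalance of √(2/50) = 0.2 SD, which is one standard error.

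| Correlation | SE without | SE with | Change | Equivalent N | Shift (points) |
|---|---|---|---|---|---|
| 0 | 0.0994 | 0.1001 | +0.7% | 99 | 0.2 |
| -0.2 | 0.0976 | 0.0968 | -0.8% | 102 | 1.6 |
| -0.3 | 0.0974 | 0.0956 | -1.9% | 104 | 2.1 |
| -0.4 | 0.0995 | 0.0955 | -4.0% | 108 | 3.0 |
| -0.5 | 0.1005 | 0.0931 | -7.3% | 116 | 3.9 |
| -0.6 | 0.0993 | 0.0868 | -12.6% | 131 | 4.8 |

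With baseline in the model the shift is 0.2 points or less throughout. The mean estimate is the same either way (for example 0.116 and 0.117 at -0.5), so there is no bias to remove.

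**Linking the two.** With equal variances, baseline-change correlation = -√((1-r)/2). So r = 0.7 gives -0.39, r = 0.5 gives -0.50 and r = 0.4 gives -0.55. The simulations agree closely at the first two. A correlation of -0.3 needs r = 1 - 2 × 0.09 = 0.82.

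**PGI-S 'Improved'.** CMH-weighted risk difference by MAC history versus SLR with history and baseline PGI-S, assuming 5-10% at baseline level 1 and latent correlation 0.4 to 0.8. The SE ratio was 0.852 to 0.920, a fall of 8-15% (equivalent N 118 to 138). The chance of 'Improved' was 0 at level 1, 0.15-0.24 at level 2, 0.43-0.57 at level 3 and 0.66-0.81 at level 4.

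**The case against.** The strongest reply is that little rests on these results. WSMC is exploratory and goes to a CSR appendix. PGI-S sits under other efficacy assessments, and SAP 7.2 disclaims inference. The mean-change analyses already give baseline-adjusted arm effects. Protocol 10.6.1 names no covariate for categorical models beyond possible strata, so the SAP departs from nothing. A half-width moving from about 19 to 18 points is unlikely to change a conclusion. All of this stands and sets the priority. It does not remove the point, because in a descriptive analysis the interval is the result.

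The size for WSMC is also uncertain. The thresholds arrive after unblinding and only for the revised scales (SAP 10.3.1), which may drop items. The QOL-B ceiling is a weak argument on its own. Protocol 4.1.1 requires "An average QOL-B respiratory domain score of ≤ 85 based on scores at Screening and on the day of enrollment prior to randomization", which leaves 15 points of room on average, about twice the assumed 7.4. For the respiratory PGI-S, entry also requires documented respiratory signs or symptoms, so level 1 should be uncommon there.

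A reader might infer that the SAP adjusts every continuous change analysis for baseline. It does not: the ANOVA/ANCOVA in SAP 11.4 lists only conversion status and treatment. The contrast holds for the arm-comparison ANCOVAs.

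A reader might also want the covariate carried into the subgroups of SAP 10.5. There the SAP drops even MAC history, with reason. Simulated under the same kind of assumptions at 5 per arm, adding baseline raised failed or extreme fits from about 12-13% to 20-28%, for an SE gain of about 0-4%. At 3 per arm such fits rose from about 44% to 62-68%.

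**Conclusion.** The omission is real in both full-sample comparisons, and nothing elsewhere in the plan makes it good. It costs precision and leaves chance imbalance uncorrected. A reader might take it as bias, but randomization balances baseline in expectation and the simulated estimates did not move.

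For WSMC the loss is about 3-7% of the standard error at pre-post correlations of 0.7 to 0.4, and negligible if the baseline-change correlation is weaker than about -0.3. That weak case needs a pre-post correlation of about 0.82 across seven months that include treatment. By comparison, Protocol 10.5.4.1 accepts 0.7 as satisfactory retest reliability in stable subjects over 30 days. For PGI-S the loss is about 8-15%. Every one of these figures depends on assumed distributions. The primary validation objective and the stated power are untouched. This is a free improvement of modest priority.

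**What to change.** - **SAP 10.3.2:** add the baseline score of the same PRO to the SLR as a continuous covariate alongside MAC history (QOL-B respiratory for the QOL-B threshold, PROMIS fatigue for the PROMIS threshold). Settle this before unblinding, since the thresholds are known only afterwards.
- **SAP 11.2.2.1:** replace or supplement the CMH test with an SLR on treatment, MAC history and baseline PGI-S, and report the standardised difference with its 95% CI. Enter baseline PGI-S as a numeric score. As a category, level 1 has no responders by definition and would cause separation in the logistic fit. Show the number of subjects per arm with baseline PGI-S = 1, for each of the two PGI-S items.
- **SAP 10.5:** leave as it is; do not require the covariate in small subgroups.

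The cost is a change of SAP wording and a few lines of programming, with data already collected and the macro already specified for the SLR.
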